5.3.4 Antimicrobial Stewardship

All patients in both arms of the study will undergo prospective audit and feedback by the institutional AS programs. The AS physician or pharmacist will review the subject’s microbiology results and medical records. The AS provider will contact the primary service (or the consulting infectious diseases (ID) physician, if applicable) if modifications

to therapy are indicated, at any time following notification of positive Gram stain result, organism identification, and/or AST results. If the ID service is consulting on the subject, the AS team will contact the ID service rather than the primary service. If the rapid test result is ready when the AS team is unavailable (i.e. in the evening or weekend), the AS team will review the record and make recommendations at the beginning of the following working day. Local institutional treatment guidelines will be followed. Recommendations will be communicated to the treating teams via telephone or pager and documented per institutional standards. Recommendation types and acceptance rates will be recorded in the study database. Categories of recommendations include: intravenous to oral conversion, de-escalation of gram negative coverage, de-escalation of gram positive coverage, escalation of gram negative coverage, escalation of gram positive coverage, dose optimization, discontinuation of therapy, therapeutic drug monitoring, reduce/define duration of therapy, ID consultation, and other. More than one stewardship recommendation category may be chosen.

In addition to prospective audit and feedback, other routine institutional AS activities will continue, such as implementation of institutional treatment guidelines, prior authorization of restricted antibiotics, review of all patients on selected antibiotics with feedback to clinicians, and daily review of specific culture results.

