5.5.1 Baseline Assessment

Once a patient is randomized, information about the patient's demographics, comorbid conditions, severity of illness (e.g. components of the Pitt Bacteremia Score¹⁸⁻²⁰), and microbiology and antimicrobial susceptibility results will be recorded. Whether a patient is on comfort care will be recorded, as determined by review of the primary physician team notes and any relevant consultations (e.g. Palliative Care).

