7.3 Sample Size

The study is designed to detect a difference in primary outcome, mean time to first antibiotic modification in the first 72 hours after randomization. We plan to enroll 500 unique participants (250 in each arm) in order to have at least 200 evaluable participants in each arm. Participants who died prior to randomization, were on comfort care at time of randomization, had GNB bacteremia at same or different institution within 7 days prior to randomization, or who were erroneously randomized due to laboratory issues such as spurious Gram stain result, will be considered unevaluable. This will provide 80% power with a 2-sided alpha=0.05 test, to detect a difference in the time to first modification of antibiotic therapy between the two arms of at least 9 hours, with a standard deviation (SD) of 32 hours. With 500 participants, if the SD is larger than 32 hours, there will still be sufficient power to detect a difference between the arms of 10 or more hours (see Table 8).

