We assume that differences in the primary outcome will be due to the rapid testing results. We anticipate that most subjects will be receiving empiric broad-spectrum antibiotic therapy at randomization, and a difference between the arms of 9 hours or more in time to antibiotic escalation or de-escalation would be reasonable based on the turn-around-time of the rapid test, and clinically relevant with regards to risks of ineffective therapy or prolonged exposure to broad-spectrum agents. Estimates for the SD for time to first modification of antibiotic therapy are based on data from subjects with GNB bacteremia from the BCID trial¹⁵. We assume that the arm including stewardship in the BCID trial (BCID test plus AS), is a reasonable surrogate for the RAPIDS standard testing arm. This is because the BCID test provided minimal susceptibility results for GNB, and did not impact time to antibiotic modifications for subjects with GNB bacteremia¹⁵. Based on the BCID trial data, in the RAPIDS standard testing arm, we expect 63% will have antibiotic de-escalation with mean time of 31 hours (SD 27), 23% will have antibiotic escalation with mean time of 18 hours (SD 21), and 14% will have no antibiotic change. Incorporating the participants with no change, we expect the overall mean time to change in the standard testing arm will be 33.75 hours (SD 28.8). We anticipate that the rapid testing arm will have similar frequencies of antibiotic de-escalation, escalation, and no change. Based on the turn-around-time of the rapid test, we estimate that mean time to antibiotic de-escalation and escalation will be approximately 12 hours (SD 24). Incorporating subjects with no antibiotic change, we expect the overall mean time to antibiotic modification in the rapid testing arm will be

20.4 hours (SD 30.5). The sample size was selected to allow the study to be well powered if this is an optimistic estimate of the standard deviation.

Table 8: Power to detect a difference in means over a range of SD for a sample size of 250 per arm/500 total (200 per arm inflated 20% for death at randomization, comfort care at randomization, GNB bacteremia at same or different institution within 7 days, laboratory errors) for a 2-sided alpha=0.05 test

Difference in means (hours)	SD = 27 h	SD = 30 h	SD = 32 h	SD = 33 h	SD = 34 h
8	84%	76%	70%	68%	65%
9	91%	85%	80%	78%	75%
10	96%	91%	88%	86%	84%
12	99%	98%	96%	95%	94%

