7.4 Analysis

7.4.1 Analysis of primary outcome

We will calculate the mean difference in time to first antibiotic modification within 72 hours post randomization in both treatment arms, together with a 95% confidence interval. Patients who do not have antibiotic modifications will be assigned a time of 72 hours. The primary test will be a t-test (relying on a normal approximation, allowing for unequal variances in the treatment groups) for whether the mean of the primary outcome is different between the arms. We will also carry out a Wilcoxon rank-sum test, to compare the distribution of the time to first antibiotic modification between the arms without the assumption of normality. We will estimate the probability of having an escalation or de-escalation of antibiotics between 0 and 72 hours after randomization using the empirical cumulative distribution function with pointwise 95% confidence intervals.

The primary analysis will be a modified intention to treat analysis (ITT). Participants who died prior to randomization, were on comfort care at randomization as assessed by the study coordinator, had GNB bacteremia at same or different institution within 7 days prior to randomization, or whose blood culture had erroneous Gram stain results in the laboratory will be considered unevaluable. These are all issues which may not be known to the laboratory technologist at the time of randomization and would otherwise be exclusion criteria. Participants randomized to the rapid testing arm will be analyzed as randomized, including cases where the rapid test does not return a result.

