APPENDIX I – Schedule of Assessments

	Screening	Enrollment/baseline	24 hours	48 hours	72 hours	30 days	Close of study
Time of blood culture	x						
Evaluation of exclusion criteria	x						
Randomization		x					
Demographics		x					
Medical history		x					
Components of Pitt Bacteremia Score ¹⁸		x					
Comfort care		x					
Antibiotic administration		x	x	x	x		
Admission information		x					
Vital signs		x					
Source of bacteremia					X ^[2]		
Results of microbial identification					x		
Results of AST					x		
Evaluation of whether stewardship recommendation made and, if so, whether accepted ^[1]			x	x	x		
Date of discharge						x	
Clostridium difficile testing results						x	
Acquisition of new target HAI or MDRO						x	
Readmission						x	
Death status through 30 days							x
Cost data through 30 days							x

Footnotes:

1. Stewardship recommendations may occur at any time between randomization and 72h post randomization.
2. As assessed by the stewardship team within 72 hours of randomization

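### The primary t-test is valid and adequately powered, but it uses neither site nor baseline values already captured, so some precision is probably given up

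*Combined protocol and SAP*

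**What the plan says.** Section 7.4.1 assigns 72 h to participants with no modification and tests the difference in means by arm: "The primary test will be a t-test (relying on a normal approximation, allowing for unequal variances in the treatment groups". A Wilcoxon rank-sum test and empirical cumulative distribution curves are added. None of these contains a covariate or a stratum term. Section 7.4.2 carries the same approach over to other mean differences.

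Section 5.2 stratifies randomization by site and by nothing else.

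Baseline information is nevertheless collected:
- Section 5.5.1 records "severity of illness (e.g. components of the Pitt Bacteremia Score" and comorbid conditions.
- Appendix I marks "Antibiotic administration" at enrollment/baseline as well as at 24, 48 and 72 hours, and also lists vital signs and admission information at baseline.
- Section 7.2.3 plans exploratory subgroups by ICU status and neutropenia at baseline, so both must be available.

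On size, Section 7.3 states: "This will provide 80% power with a 2-sided alpha=0.05 test", for a difference "of at least 9 hours, with a standard deviation (SD) of 32 hours", enrolling 500 "in order to have at least 200 evaluable participants in each arm".

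**The concern.** Some baseline values should predict the outcome on the plan's own logic. The outcome is the first change from the current regimen, and Section 7.1 defines escalation and de-escalation largely as moves up or down Tables 5 and 6. The starting regimen therefore limits which changes are possible. Weekday may matter too: under Section 5.3.4, when a rapid result is ready in the evening or at a weekend, "the AS team will review the record and make recommendations at the beginning of the following working day".

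If such values are prognostic, an unadjusted comparison leaves the interval wider than it needs to be and leaves chance imbalance in baseline regimen uncorrected. Leaving out site, when randomization is balanced within site, tends to make the standard error conservative if the sites differ in mean time to modification. The trial is sized at 80% power for its design difference, so any lost precision matters most there.

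**Working it through.** **Inputs (Section 7.3).** Difference 9 h, SD 32 h, 200 evaluable per arm, two-sided alpha 0.05. Expected standard arm: 63% de-escalated at 31 h (SD 27), 23% escalated at 18 h (SD 21), 14% unchanged. Expected rapid arm: 86% changed at 12 h (SD 24), 14% unchanged. Section 7.4.1 scores unchanged as 72 h.

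**1. The plan's own figures.**
- Standard arm mean: 0.63×31 + 0.23×18 + 0.14×72 = 33.75 h; variance 827.3, SD 28.76 h.
- Rapid arm mean: 0.86×12 + 0.14×72 = 20.40 h; variance 928.8, SD 30.48 h.
- Standard error at SD 32 h: 32×√(2/200) = 3.2 h. Power for 9 h from the noncentral t with 398 degrees of freedom: 80.1% (stated: 80%).
- All 20 cells of Table 8 reproduce within one percentage point at 200 per arm.

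**2. Power at the expected effect.** Difference 33.75 − 20.40 = 13.35 h; root-mean-square SD √((827.3 + 928.8)/2) = 29.63 h. Unadjusted power is 99.4%.

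**3. Effect of adjustment.** Residual SD = 32×√(1 − R²); half-width = 1.966 × residual SD × √(2/200). The documents give no R², so these values are assumed:

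| R² (assumed) | Residual SD (h) | Power for 9 h | 95% CI half-width (h) |
|---|---|---|---|
| 0 | 32.00 | 80.1% | 6.29 |
| 2% | 31.68 | 80.9% | 6.23 |
| 5% | 31.19 | 82.1% | 6.13 |
| 10% | 30.36 | 84.1% | 5.97 |

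An R² of 5% is worth about 11 more evaluable participants per arm (200/0.95 = 211), and 10% about 22 (200/0.90 = 222).

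**4. What R² might regimen alone give?** Suppose a share p is on a narrow regimen, with a fraction u of them unchanged and a fraction w unchanged among the rest, keeping 14% unchanged overall. If changers have the same mean time whatever their regimen, R² = p(1−p)[(u−w)(72−m)]²/variance. Here m, the mean among changers, is (0.63×31 + 0.23×18)/0.86 = 27.52 h in the standard arm and 12 h in the rapid arm. All p and u are assumed, with u from 35% to 45%:
- p = 10–15%: R² about 1.2–4.1% (standard) and 1.9–6.6% (rapid).
- p = 25–30%: R² about 3.5–10% (standard) and 6–16% (rapid).

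For example, with p = 25% and u = 40%, w = (0.14 − 0.10)/0.75 = 0.053, and standard-arm R² = 0.1875×(0.347×44.48)²/827.3 = 5.4%.

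**5. An offsetting effect.** Participants on a narrow regimen may be escalated more often, and the plan expects escalation to come sooner than de-escalation. Take p = 25%, with 40% of them unchanged, 50% escalated and 10% de-escalated (assumed). Their mean is 0.40×72 + 0.50×18 + 0.10×31 = 40.9 h. The rest then average (33.75 − 0.25×40.9)/0.75 = 31.37 h. Standard-arm R² = 0.1875×(40.9 − 31.37)²/827.3 = 2.1%, down from 5.4%.

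**The case against.** The strongest reply is that nothing is broken. An unequal-variance t-test is valid in a randomized trial, simple and transparent. The sizing is cautious: SD 32 h is used against expected values of 28.8 and 30.5 h, and power at the expected effect is 99.4%. With no documented R-squared, the gain could be close to nil. All of this stands, and it limits the point to efficiency. It does not remove the point, because the trial is sized for 9 h, where power is 80%, and the cost of adjusting is very small.

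Three stronger readings are tempting, and the documents do not support them.

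- **That a large share of the variance is recoverable.** Section 7.3 expects that "14% will have no antibiotic change". The changed/unchanged split accounts for 0.86×0.14×(72 − 27.52)²/827.3 = 29% of the variance in the standard arm and 0.86×0.14×(72 − 12)²/928.8 = 47% in the rapid arm. That split is observed after randomization and is part of the outcome. It is not a baseline covariate, and it does not give an achievable R-squared.
- **That hour and weekday are recorded baseline items.** Appendix I lists neither; they can only be derived from the randomization time stamp. Enrollment is confined to laboratory business hours (Section 4.1), which narrows the range of hour. The delay in Section 5.3.4 is worded for the rapid result, so it may alter the effect of testing as much as it predicts outcome in both arms.
- **That Pitt score and ICU status are known predictors.** No passage shows that either predicts time to modification.

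**Conclusion.** The point holds as an efficiency improvement. The primary analysis is sound and adequately powered as written, but it ignores the only stratification factor and baseline values already in hand, so some precision is probably lost. Under an assumed R-squared of 2% to 10%, the gain at the design difference is 0.8 to 4.0 percentage points of power and 0.06 to 0.32 h of CI half-width. At the expected 13.35 h it is a narrower interval and nothing else of substance. That plan-level absence of adjustment is certain; the size of the loss is not, and it depends on how many participants start on narrow regimens and how they are then managed. A reader should not infer that the t-test is wrong or the trial underpowered.

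**What to change.** Before outcome data are seen by arm, prespecify in Section 7.4.1 that the primary estimate is the arm coefficient, with its 95% CI and test, from a linear model for the 72 h-capped time. Use heteroscedasticity-robust (HC3) standard errors, which keep the allowance for unequal variances. Adjust for:
- site;
- regimen in use at or before the randomization time: none, or the highest Table 5 category; any Table 6 agent, yes/no;
- ICU at baseline;
- Pitt score.

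The regimen cut-off must be explicit, because Section 7.2.3 recognizes that antibiotics may change within the first hour in response to the Gram stain; changes after the randomization time must not enter the covariate. State one simple rule for missing covariates, applied without regard to arm. Weekday of randomization (weekend or pre-weekend, yes/no), derived from the time stamp, may be added.

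Keep the Welch t-test and the Wilcoxon test as supportive analyses. The estimand, the difference in mean hours, does not change. The cost is SAP wording and a few degrees of freedom out of about 400, with no new data items and no more participants. The timing matters because adjustment added after unblinding would look data-driven.

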5.3 Interventions

5.3.1 Notifications

Once study group is assigned, the Laboratory Technologists will immediately notify the Study Coordinator via electronic or telephone page. The Study Coordinator will then notify the Antimicrobial Stewardship (AS) team that a subject has been randomized to either arm. Each subject's medical record number, group assignment and subject ID will be recorded in an electronic log.

For subjects in both arms, the Laboratory Technologists will notify ordering clinicians by telephone when the Gram stain results are available, as is done in routine clinical practice.

Sites are responsible for notifying appropriate agencies of reportable infectious diseases per institutional policy.

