5.4 Blinding

Primary service/provider: The primary service, including the prescribing provider, will be unaware of group assignment at the time of randomization, so initial antibiotic choice will not be affected by group assignment. Once rapid results become available and/or AS interventions are made, treating providers may become aware of group assignment.

The AS team and laboratory technologists will not be blinded.

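### Could the comfort-care and Gram-stain removals from the modified ITT set differ by arm and bias the primary comparison?

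*Combined protocol and SAP*

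**What the plan says.** The primary analysis (7.4.1) is a modified intention-to-treat analysis. Four kinds of randomised patient are set aside: those who died before randomisation, those who "were on comfort care at randomization as assessed by the study coordinator", those with gram-negative bacteremia in the previous 7 days at any institution, and those "whose blood culture had erroneous Gram stain results in the laboratory will be considered unevaluable". The stated reason is: "These are all issues which may not be known to the laboratory technologist at the time of randomization and would otherwise be exclusion criteria". Section 7.3 words the laboratory item more loosely, as patients "who were erroneously randomized due to laboratory issues such as spurious Gram stain result".

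On who knows the group, 5.3.1 says: "Once study group is assigned, the Laboratory Technologists will immediately notify the Study Coordinator via electronic or telephone page". It continues: "The Study Coordinator will then notify the Antimicrobial Stewardship (AS) team that a subject has been randomized to either arm". Group assignment is also entered in an electronic log. Under 5.4 the stewardship team and the technologists are unblinded, and the coordinator is not mentioned. Of the clinicians, 5.4 says: "The primary service, including the prescribing provider, will be unaware of group assignment at the time of randomization". It adds that later on "treating providers may become aware of group assignment".

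Comfort-care status comes from the primary team's notes and relevant consultations (5.5.1) and is scheduled at baseline (Appendix I). Sections 5.3.2 and 5.3.3 give the detailed Gram-stain rules. The exploratory list in 7.2.3 and the text of 7.4.2 contain no analysis of all randomised patients.

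**The concern.** Removing patients for a condition that existed before randomisation is unbiased only if the condition is looked for in the same way in both arms. Two features raise doubt.

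- **Comfort care.** The person who decides is contacted after allocation and probably knows the group, although 5.3.1 does not say that the page names it. The chart is abstracted after randomisation, and 5.5.1 does not require the notes used to pre-date it.
- **Gram stain.** Section 4.2 excludes a stain showing gram-negative bacilli plus another organism, and 7.4.1 says its removals would otherwise be exclusions. In the rapid arm, an extra organism found by the rapid test makes an unblinded technologist re-read the stain (5.3.3). No such re-read is described for the standard arm. Read literally, a missed second organism found this way is an erroneous stain, and the patient might be dropped while a like patient in the standard arm stays in.

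The primary comparison is at stake. Patients without a modification score 72 h, so a few one-sided removals at that value would move the mean difference, and no planned table or analysis would show it.

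**Working it through.** **1. The plan's own figures.** With 9 h, SD 32 h, two-sided alpha 0.05 and 80% power (7.3), n per arm = 2 × (1.960 + 0.842)² × 32² / 9² = 198.5, so 199 against the 200 stated. Power at 200 per arm is 80.1% by the t-test. Inflation: 200 / 0.80 = 250. Standard-arm mean: 0.63 × 31 + 0.23 × 18 + 0.14 × 72 = 33.75 h. All agree with the document, so the question is only who is in the analysis set.

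**2. The Gram-stain wording side by side.**

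| Situation | Section | Stated consequence |
|---|---|---|
| Standard culture grows other organisms instead of gram-negative bacilli | 5.3.2, both arms | Unevaluable |
| Rapid test finds other organisms instead | 5.3.3 | Rapid result withheld; unevaluable if standard culture shows other organisms instead |
| Rapid test finds another organism in addition, seen on re-read | 5.3.3 | Listed organisms reported; nothing said about evaluability |
| Rapid test finds another organism in addition, not seen on re-read | 5.3.3 | Not reported; nothing said about evaluability |

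Wherever the detailed sections call a patient unevaluable, standard culture decides, and every patient has it (5.3.2). The stated reason is that the patient does not have gram-negative bacteremia. A patient with an additional organism still has it. The short phrases in 7.3 and 7.4.1 read naturally as summaries of this rule. Even on the broad reading, a standard-arm culture that grew an extra organism would also show that the stain had missed one, so removals would not be confined to the rapid arm.

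**3. Comfort care.** Three provisions constrain the decision: the status is that at randomisation (7.4.1), it is a baseline item (Appendix I), and its source is the notes of clinicians unaware of the group at that time (5.5.1, 5.4). Bias would need the coordinator to misread a documented status differently by arm.

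**4. How large could one-sided removal be?** Assumptions, none from the documents except 33.75 h, SD 32 h and 200 per arm: no true effect, and k patients with score v wrongly removed from the rapid arm only.

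- Shift = k × (v − 33.75) / (200 − k)
- SE = 32 × √(1/200 + 1/(200 − k))
- Two-sided type I error = P(|Z + shift/SE| > 1.96)

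| k | SE (h) | v = 72 h: shift, error | v = 50 h: shift, error | v = 0 h: shift, error |
|---|---|---|---|---|
| 2 | 3.208 | 0.39 h, 5.2% | 0.16 h, 5.0% | −0.34 h, 5.1% |
| 5 | 3.220 | 0.98 h, 6.1% | 0.42 h, 5.2% | −0.87 h, 5.8% |
| 10 | 3.242 | 2.01 h, 9.5% | 0.86 h, 5.8% | −1.78 h, 8.5% |

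Positive shifts favour rapid testing. Scores lie between 0 and 72 h, so the 72 h and 0 h columns are outer limits for each k. Ten patients at 72 h would be 10 / (0.14 × 200) = 36% of the no-change patients expected in that arm.

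**5. What an all-randomised analysis would add.** With 250 per arm and SD 32 h, power for a 9 h effect is 88%. If 10% of patients contribute no effect, the difference is 0.9 × 9 = 8.1 h and power 81%; if 20%, it is 0.8 × 9 = 7.2 h and power 71%. The result can therefore differ from the primary one through dilution alone, without any uneven removal.

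**The case for a change.** The strongest case for a change is the Gram-stain wording. No sentence says that a patient with a mixed stain on re-read stays in. Sections 4.2 and 7.4.1 together permit the opposite reading, 7.3 is open-ended, and only the rapid arm has the stated trigger. The plan allows 50 of 250 patients per arm to be unevaluable, so one can fairly ask that even-handed removal be shown and not assumed. The costs look small: some wording, a reviewer without access to the group log at each of two sites, one sensitivity analysis and one table.

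The ambiguity stands as a matter of wording, and masking is indeed not stated. The remedies gain little, however.

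- Defining the Gram-stain rule by standard culture writes down what 5.3.2 and 5.3.3 already say.
- A separate reviewer is a real burden in a two-site study based on routine records. If prior bacteremia had to be judged only from records dated up to randomisation, an episode at another hospital documented later could be missed, which is the kind of late-known fact 7.4.1 provides for.
- The all-randomised analysis mixes dilution with uneven removal, cannot tell them apart, and leaves the primary result as it is.

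The direction is unclear too. If an extra organism is confirmed and reported, adding an antibiotic counts as escalation (7.1.1), so some of these patients could have early times. Removing them would work against rapid testing.

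**Conclusion.** The concern does not call for a change. The documents plan no arm-dependent removal, and the detailed sections supply a rule that works alike in both arms. The loose phrases in 7.3 and 7.4.1 are a gap that analysts would fill sensibly from 5.3.2 and 5.3.3: an additional organism does not make a patient unevaluable. A count of removals by arm and reason is ordinary participant-flow reporting and needs no amendment; an all-randomised analysis is optional.

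The size of any bias cannot be estimated, because the documents give neither counts by reason nor outcomes of removed patients. The limits above, 0.3 to 0.4 h for 2 patients and 1.8 to 2.0 h for 10, rest on wrongful removal from one arm only with every score at an extreme. They are remote bounds, not forecasts. The conclusion assumes that the detailed rules govern the summary wording and that comfort-care status is abstracted as it stood at randomisation. A marked imbalance in removals for either reason would reopen the question.
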